#### **6.3.2 Criteria for Premature Termination or Suspension of Study Sites**

A study site may be terminated prematurely or suspended if the site (including the investigator) is found in significant violation of GCP, protocol, or contractual agreement, is unable to ensure adequate performance of the study, or as otherwise permitted by the contractual agreement.

#### **6.3.3 Procedures for Premature Termination or Suspension of the Study or the Participation of Study Sites**

In the event that the sponsor, an Institutional Review Board (IRB), or a regulatory authority elects to terminate or suspend the study or the participation of a study site, a study-specific procedure for early termination or suspension will be provided by the sponsor; the procedure will be followed by applicable study sites during the course of termination or study suspension.

## 7.0 SELECTION AND DISCONTINUATION/WITHDRAWAL OF SUBJECTS

All entry criteria, including test results, need to be confirmed before the first dose of study drug.

### 7.1 Inclusion Criteria

Subject eligibility is determined according to the following criteria before entry into the study:

1. In the opinion of the investigator, the subject or subject's legally acceptable representative is capable of understanding and complying with protocol requirements.
2. The subject or the subject's legally acceptable representative signs and dates a written, informed consent form and any required privacy authorization before the initiation of any study procedures, including requesting that a subject fast for any clinical laboratory evaluations. An assent should be obtained from the subject, if possible. If the subject cannot provide assent (ie, due to developmental status), the investigator should document why assent was not obtained. For subjects with G-tube/PEG tube, a separate supplemental consent form will be signed by the subject/caregiver and attached to the general consent.
3. The subject is a male or female aged  $\geq 18$  and  $\leq 65$  years at the time of informed consent and the first dose of study drug.
4. The subject has a documented clinical diagnosis of developmental and/or epileptic encephalopathies with bilateral motor seizures, defined as an average of  $\geq 2$  per month during the past 3 months, based on the investigator's assessment, and a monthly average of  $\geq 1$  per month during the 4-week Baseline Period, based on the seizure diary record.

Developmental and/or epileptic encephalopathy will be defined as:

- Subjects with an established diagnosis of the following: for example, Lennox-Gastaut Syndrome, Dravet Syndrome, Tuberous Sclerosis Complex, OR
- Retrospectively including:
  - History of special education classes, OR
  - Formal IQ  $< 70$ , OR
  - Generalized background slowing (posterior dominant rhythm [PDR] persistently  $< 8$  Hz) on interictal EEG,

AND

- Epilepsy not due to a brain injury acquired after age 3 years.
5. The subject is taking 1 to 4 AEDs at a stable dose for  $\geq 4$  weeks before Screening (Visit 1), and the subject or subject's legally acceptable representative is willing to keep the regimen(s) stable throughout the study. For the purposes of this study ketogenic diet and vagus nerve stimulation will not be considered AEDs.

6. The subject has an average of  $\geq 1$  bilateral motor seizure per month during the 4-week Baseline Period (ie, drop seizures, tonic-clonic, tonic, bilateral clonic, atonic, myoclonic-atonic, myoclonic-tonic-clonic, focal seizures with bilateral hyperkinetic motor features). Drop seizures are defined as a seizure involving the entire body, trunk or head that leads to a fall, injury, slumping in a chair, or head hitting the surface, or could have led to a fall or injury, depending on the position of the subject at the time of the attack or spell. Drop seizures will be captured separately (eg, tonic seizures leading to a drop will be captured as a drop). If the subject has  $< 1$  bilateral motor seizure per month during the Baseline Period, the subject will be considered a screen failure.
7. A female subject of childbearing potential\* must have a negative serum pregnancy (human chorionic gonadotropin [hCG]) test at Screening (Visit 1) and a negative urine pregnancy test before Randomization (Visit 2). If urine cannot be collected, the results of the serum pregnancy test obtained at Visit 1 must be confirmed to be negative by the investigator prior to randomization.
8. A female subject of childbearing potential\* who is sexually active with a nonsterilized\* male partner agrees to use routinely an adequate method of contraception\* from signing of informed consent throughout the duration of the study and for 30 days after last dose.
9. A male subject who is nonsterilized\* and sexually active with a female partner of childbearing potential\* agrees to use adequate contraception\* from signing of informed consent throughout the duration of the study and for 30 days after last dose.

\*Definitions and acceptable methods of contraception are defined in Section 9.1.12 and reporting responsibilities are defined in Section 9.1.13.

10. Subjects and/or subjects' caregivers must agree to not post any subject's personal medical data related to the study or information related to the study on any web site or social media site (eg, Facebook, Twitter) until the study has been completed.
11. For subjects with G-tube/PEG tube, G-tubes/PEG tubes should have been placed and been functioning for at least 3 months prior to screening. Naso-gastric tubes are not allowed.

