## 6.0 STUDY DESIGN AND DESCRIPTION

### 6.1 Study Design

This phase 1b/2a, multicenter, randomized, double-blind, placebo-controlled, parallel-group, dose-escalation study with an open-label part is designed to examine the safety, tolerability, PK, and PD of TAK-935 as adjunctive therapy in adult subjects with a diagnosis of developmental and/or epileptic encephalopathies. This study will be conducted at approximately 11 sites in North America with experience in conducting clinical studies in patients with rare epilepsies.

Adult subjects (aged  $\geq 18$  and  $\leq 65$  years) with a diagnosis of developmental and/or epileptic encephalopathies demonstrating bilateral motor seizures (ie, drop seizures, tonic-clonic, tonic, bilateral clonic, atonic, myoclonic-atonic, myoclonic-tonic-clonic, focal seizures with bilateral hyperkinetic motor features) (average of  $\geq 2$  per month during the past 3 months) based on the investigator's assessment will be enrolled. The study will screen a sufficient number of subjects to ensure approximately 20 randomized subjects.

At the Screening Visit (Visit 1), informed consent and/or assent (if applicable) is obtained from the subjects and/or subjects' legally acceptable representative. Subjects will then undergo screening procedures to assess study eligibility in accordance with the study entry criteria (see [Appendix A](#) and Sections 7.1 and 7.2). CCI

The 4-week Baseline Period CCI can begin as soon as informed consent has been signed. At the end of the 4-week Baseline Period and after confirmation of eligibility, subjects will return to the clinic on Day 1 in Part 1 (Visit 2) for randomization. If a subject does not meet the eligibility criteria during the Screening/Baseline Period, the subject will be discontinued from the study (screen failure).

The study will consist of 2 parts:

- Part 1 is a randomized double-blind part consisting of 3 periods: a screening/baseline period (4-6 weeks), titration period (20 days), and maintenance period (10 days). The target final dose of 300 mg BID will be reached after a 20-day titration period.
- Part 2 is an open-label continuation part consisting of 4 periods: a titration period (10 days), maintenance period (44 days), de-escalation period (3-6 days) and follow-up period (30 days).

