**Table 9.a Approximate Blood Volume**

Sample Type	Sample Volume (mL)	Number of Samples (a)			Total Volume (mL)
		Screening Visit	Part 1	Part 2	
HIV, HBsAg, HCV (b)	6	1	---	---	6
HCV RNA detection by qPCR (c)	6	1	---	---	6
FSH (d)	(d)	1		1	(d)
Estradiol (e)	2	1		1	4
Serum chemistry (f)	6	1	1	2	24
Hematology	2	1	1	2	8
Plasma sample for TAK-935 PK analysis	4	---	8	3	44
Plasma sample for AED analysis	4	---	3	3	28
Plasma sample for PD analysis (g)	4	2	16	6	104
Blood sample for DNA PGx	6	---	1	---	6
Blood sample for RNA PGx (g)	2.5	---	2	2	10
Total Blood Volume (mL)					240

--- =not applicable.

(a) Does not include blood draws at any unscheduled visits.

(b) One 2-mL blood sample for each test.

(c) Subjects who are positive for hepatitis C Ab should return to the clinic for an unscheduled visit to provide a blood sample for HCV qPCR.

(d) For diagnostic purposes in female subjects only; sample will be run from serum chemistry volume (no extra volume required).

(e) In female subjects only.

(f) Includes serum pregnancy test for female subjects of childbearing potential.

(g) Two blood samples per scheduled time.

The clinical laboratory tests to be performed are listed in [Table 9.b](#).

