**Abstinence:**

- Sexual abstinence, if it is the preferred and usual lifestyle of the subject, will be considered an acceptable method of contraception on a case-by-case basis upon prior approval by the Medical Monitor. Subjects practicing abstinence as a method of contraception must refrain from heterosexual intercourse throughout the duration of the study and for 30 days after last dose of study drug.

Subjects will be provided with information on acceptable methods of contraception as part of the subject informed consent process and will be asked to sign a consent form stating that they understand the requirements for avoidance of pregnancy, donation of ova, and sperm donation during the course of the study and for 30 days after the last dose of study drug. This may be signed by the legal representative of the subject.

All female subjects of childbearing potential must have a negative serum hCG pregnancy test at Screening (Visit 1) and a negative urine hCG pregnancy test on Day 1 (Visit 2), before receiving any dose of study drug. During the course of the study, subjects will receive continued guidance with respect to the avoidance of pregnancy and sperm donation as part of the study procedures. An additional serum hCG pregnancy test will be performed at the Final Visit.

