**Footnotes for Appendix A**

(a) The 4-week baseline seizure diary recording can begin as soon as the ICF has been signed. Randomization can occur once the 4-week baseline seizure count of  $\geq 1$  has been obtained and the subject meets all of the inclusion and none of the exclusion criteria.

(b) Three days after each dose up-titration or de-escalation, subjects will be contacted by phone to monitor study drug compliance, concomitant medication use, and AEs.

(c) Subjects who do not enter Part 2 or withdraw early from the study should complete all procedures scheduled for the Final Visit (Visit 7) at time of withdrawal, including dose de-escalation as appropriate, followed by the Follow-up Period (Visits 8 and 9). See Section 6.1 for details.

(d) Dose de-escalation, as appropriate, begins at the Final Visit (ie, if at TAK-935 300 mg BID level, reduce to 200 mg BID for 3 days followed by 100 mg BID for 3 days; if at the 200 mg BID level, reduce to 100 mg BID for 3 days; if at the 100 mg BID level, there is no de-escalation). See Section 6.1 for details.

(e) If urine cannot be collected, the reason should be documented in the source document.

(f) Subjects who are positive for hepatitis C Ab should return to the clinic for an unscheduled visit to provide a blood sample for HCV qPCR.

(g) If the subject is unable to comply with the C-SSRS due to developmental status, a parent proxy may be used for the completion of the C-SSRS. The investigator may also use clinical judgment to assess for suicidal ideation and behavior.

(h) For female subjects only at the Screening and Final Visits.

(i) For female subjects of childbearing potential, a serum pregnancy (hCG) test will be performed at the Screening and Final Visits and a urine pregnancy test will be performed before the morning dose on Day 1 in Part 1 (Visit 2). If urine cannot be collected, the reason should be documented in the source document and the serum pregnancy test obtained at Visit 1 must be confirmed to be negative by the investigator prior to randomization. Additional pregnancy tests may be performed throughout the study at the investigator's discretion.

(j) PE must be captured in the source document. Any clinically significant abnormalities noted prior to administration of study drug should be described and captured on the Medical History form. Any clinically significant changes in PE noted after administration of study drug should be captured on the AE page of the eCRF.

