  - c) that personal information (including personal health information) may be added to Takeda's research databases for purposes of developing a better understanding of the safety and effectiveness of the study drug(s), studying other therapies for patients, developing a better understanding of disease, and improving the efficiency of future clinical studies;
  - d) that subjects agree not to restrict the use and disclosure of their personal information (including personal health information) upon withdrawal from the study to the extent that the restricted use or disclosure of such information may impact the scientific integrity of the research; and

- e) that the subject's identity will remain confidential in the event that study results are published.
25. Female subjects of childbearing potential (eg, nonsterilized, premenopausal female subjects) who are sexually active must use highly effective contraception (as defined in the informed consent) from Screening throughout the duration of the study, and for 30 days after last dose. Regular pregnancy tests will be performed throughout the study for all female subjects of childbearing potential. If a subject is found to be pregnant during study, study drug will be discontinued and the investigator will offer the subject the choice to receive unblinded treatment information.
  26. Male subjects must use highly effective contraception (as defined in the informed consent) from signing the informed consent throughout the duration of the study, and for 30 days after last dose. If the partner or wife of the subject is found to be pregnant during the study, the investigator will offer the subject the choice to receive unblinded treatment information.
  27. A statement that clinical trial information from this trial will be publicly disclosed in a publicly accessible website, such as [ClinicalTrials.gov](http://ClinicalTrials.gov).

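### When urine cannot be collected on Day 1, inclusion 7 accepts a Visit 1 serum pregnancy result that is about 4 to 6 weeks old; Section 9.1.12 allows no such exception, and the rules must be reconciled.

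*Protocol*

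**What the plan says.** The protocol states two rules for the pregnancy test before the first dose.

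- **Section 9.1.12** is unconditional. Its sentence begins "All female subjects of childbearing potential must have a negative serum hCG pregnancy test at Screening (Visit 1" and goes on to require "a negative urine hCG pregnancy test on Day 1 (Visit 2), before receiving any dose of study drug". It does not say what happens if urine is unavailable.
- **Section 7.1, inclusion 7** sets the same two tests and then adds an exception: "If urine cannot be collected, the results of the serum pregnancy test obtained at Visit 1 must be confirmed to be negative". Section 9.1.11, Table 9.b footnote (f) and SAP Table 7.f footnote (f) carry the same exception. So does Appendix A footnote (i): "the serum pregnancy test obtained at Visit 1 must be confirmed to be negative by the investigator prior to randomization".

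Sections 9.1.11 and Table 9.b footnote (a) name the expected reasons for having no urine: limited cooperation and diapers.

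On timing, Section 6.1 describes Part 1 as having "a screening/baseline period (4-6 weeks), titration period (20 days), and maintenance period (10 days", and says: "At the end of the 4-week Baseline Period and after confirmation of eligibility, subjects will return to the clinic on Day 1". Appendix A puts screening at Days -41 to 0. It schedules pregnancy tests at Screening (serum), Day 1 (urine) and the Final Visit (serum). Footnote (i) leaves any further test to the investigator. Appendix C item 25, on the content of the consent form, says: "Regular pregnancy tests will be performed throughout the study for all female subjects of childbearing potential".

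**The concern.** Re-confirming the Visit 1 result adds nothing. Inclusion 7 already required that result to be negative, and it was obtained before the baseline period ran. A woman who conceives during baseline and cannot give urine on Day 1 therefore meets inclusion 7 as written. Yet exclusion 16 bars pregnant women, and Section 7.0 asks for all entry criteria, test results included, to be confirmed before the first dose. For this subgroup no scheduled test does that.

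The two rules also give different answers for the same woman, and Section 14.2 allows no exemptions from the entry criteria. What is at stake is fetal exposure to study drug and late discovery of a condition for which Sections 7.5 and 9.1.13 require immediate withdrawal. No endpoint or analysis is affected.

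**Working it through.** **Age of the Visit 1 serum result on Day 1**

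Inputs: a 4-week baseline that can start once consent is signed (Section 6.1); a screening/baseline period of 4 to 6 weeks (Section 6.1); a screening window of Days -41 to 0 (Appendix A); study day before dosing equal to assessment date minus first-dose date (SAP Section 7.1.1).

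- Minimum: 4 × 7 = 28 days.
- Maximum, counting a Day 0 as Appendix A does: 1 − (−41) = 42 days. This equals 6 × 7 = 42 and reproduces the plan's 6-week upper limit.
- Maximum under the SAP convention, which has no Day 0: 41 days.

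The 28-day minimum assumes that the serum sample is taken on the day of consent. A sample taken later in screening would be younger.

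**Time to the next scheduled test**

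| Course | Next scheduled test | Days from Day 1 | Days from Visit 1 test |
|---|---|---|---|
| Continues into Part 2 | Final Visit, Day 85 | 85 − 1 = 84 | 28 + 84 = 112 to 42 + 84 = 126 |
| Completes Part 1 only | Final Visit procedures, Day 31 | 31 − 1 = 30 | 28 + 30 = 58 to 42 + 30 = 72 |
| Withdraws early | Final Visit procedures at withdrawal | varies | varies |

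With the ±2-day visit window, the first row becomes 110 to 128 days. Under the SAP day count its upper end is 41 + 84 = 125 instead of 126.

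**Exposure before the Day 85 test, for a woman who continues**

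- Randomised to TAK-935: 30 days in Part 1 + 10 + 44 days in Part 2 = 84 days on TAK-935.
- Randomised to placebo: placebo ends at Day 30, then 10 + 44 = 54 days on TAK-935.

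**Could a Day 1 serum sample replace the urine test?**

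Section 6.1 has blood drawn before the Day 1 dose, and Appendix A schedules clinical laboratory tests that day. Table 9.a footnote (f) says of the serum chemistry volume: "Includes serum pregnancy test for female subjects of childbearing potential". So a sample is feasible. However, Section 9.1.11 sends chemistry to a central laboratory and gives no turnaround, while Section 9.3.3 has the first dose given in clinic that same morning. The documents do not show that a result would arrive in time.

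**The case against.** The strongest reply is that the exception is deliberate. It stands in four places in the protocol and one in the SAP. Sections 9.1.22 and 9.3.2 make the inclusion and exclusion criteria decide entry, and inclusion 7 points to Section 9.1.12 for contraception definitions, not for the testing rule. On this view Section 9.1.12 is a general sentence that omits a stated exception. That is a fair reading, and it means one cannot claim that sites would in practice refuse such a woman. The texts still conflict, and repeating the exception does not make an old result current.

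The second reply is that other safeguards exist. Entry criteria are checked again at Visit 2, contraception is required from consent for sexually active women, counselling is scheduled from Screening through Day 91, and the investigator may order extra tests. These reduce the risk, so it should not be described as unmitigated. None of them requires a new test before the first dose.

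Two stronger readings are tempting and fail:

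- **That the remedy is free because blood is drawn on Day 1 anyway.** The missing turnaround time defeats this. The Table 9.a footnote applies to the whole chemistry row, and serum hCG is scheduled only at Screening and the Final Visit, so the footnote does not show that a Day 1 serum hCG is already provided for.
- **That any affected woman would take TAK-935 or placebo untested until Day 85.** Placebo stops at Day 30, and women who do not continue or who withdraw are tested at their own Final Visit.

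Lastly, the study randomises about 20 subjects, so few women can be affected. That limits the scale of the point but does not remove it.

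**Conclusion.** The point holds as an internal contradiction with a safety consequence. Section 9.1.12 requires a Day 1 result from every woman of childbearing potential. The other passages accept a result 28 to 42 days old (41 under the SAP count), which gives no information on pregnancy status at first dose. The gap between scheduled tests is 112 to 126 days for women who reach Day 85 and 58 to 72 days for those who stop at Day 31, absent a discretionary test.

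This rests on the serum sample being drawn at consent and on urine being unavailable on Day 1. The documents do not say how many women that would be. The Appendix C statement is a smaller, separate mismatch: regular is not defined there, but three scheduled tests, with none between Day 1 and the Final Visit, do not clearly match it. The documents do not settle which testing rule should prevail, and this review takes no position on that.

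**What to change.** Reconcile inclusion 7, Section 9.1.11, Table 9.b footnote (f), Appendix A footnote (i) and SAP Table 7.f footnote (f) with Section 9.1.12, so that all six places state one rule. In doing so, the sponsor should address explicitly that the Visit 1 result does not show pregnancy status at first dose, and say how exclusion 16 and Section 7.0 are satisfied when urine cannot be collected. Separately, align Appendix C item 25 with the test schedule in Appendix A, so that subjects are told what will actually be done.

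The cost is wording in the protocol and the SAP, with a check of the consent text. If the sponsor chooses a rule that needs a fresh result, a serum sample is possible at Visit 2. Because no turnaround is stated, dosing might be delayed for the few women concerned. No sample size, endpoint or analysis changes.

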## 7.2 Exclusion Criteria

Any subject who meets any of the following criteria will not qualify for entry into the study:

1. The subject has been part of a clinical study involving another investigational product in the previous 3 months or subject is currently receiving an investigational product.
2. The subject has received TAK-935 in a previous clinical study or as a therapeutic agent.
3. The subject was admitted to a medical facility for treatment of status epilepticus requiring mechanical respiration within 3 months before Screening (Visit 1).
4. The subject had a vagal nerve stimulator implanted within 6 months before Screening (Visit 1) and settings have been changed within 1 month of the Screening Visit (Visit 1) and/or are anticipated to change during the study.

5. The subject is on a ketogenic diet that has been started within 6 months of the Screening Visit (Visit1), has been changed within 1 month of the Screening Visit (Visit 1), or is anticipated to change during the study.
6. The subject is an immediate family member, study site employee, or is in a dependent relationship with a study site employee who is involved in the conduct of this study (eg, spouse, parent, child, sibling) or may consent under duress.
7. The subject has unstable, clinically significant neurologic (other than the disease being studied), psychiatric, cardiovascular, pulmonary, hepatic, renal, metabolic, gastrointestinal, urologic, immunologic, hematopoietic, or endocrine disease or other abnormality, which may impact the ability of the subject to participate or potentially confound the study results. It is the responsibility of the investigator to assess the clinical significance; however, consultation with the Medical Monitor may be warranted.
8. The subject has degenerative eye disease.
9. The subject has a history of suicidal behavior or any suicidal ideation of type 4 or 5 on the C-SSRS at Screening (Visit 1). If the subject is unable to comply with the C-SSRS due to developmental status, a parent proxy may be used for the completion of the C-SSRS. The Investigator may also use clinical judgment, which must then be documented in the source document.
10. Positive for human immunodeficiency virus, hepatitis B, or hepatitis C infections. (Note that subjects who have been vaccinated against hepatitis B [hepatitis B surface antibody {Ab}-positive] who are negative for other markers of prior hepatitis B infection [eg, negative for hepatitis B core Ab] are eligible. Also note that subjects who are positive for hepatitis C Ab are eligible as long as they have a negative hepatitis C viral load by quantitative polymerase chain reaction [qPCR]).
11. The subject has an abnormal and clinically significant ECG at Screening (Visit 1), in the opinion of the investigator, for example, second or third-degree heart block or a corrected QT interval (QTc) >450 msec. Entry of any subject with an abnormal but not clinically significant ECG must be approved and documented by signature by the principal investigator or appropriately qualified delegate.
12. The subject has abnormal clinical laboratory test results at Screening (Visit 1) that suggest a clinically significant underlying disease. If the subject has alanine aminotransferase (ALT) and/or aspartate aminotransferase (AST) >2.5 × the upper limit of normal (ULN), the Medical Monitor should be consulted.
13. The subject has a known hypersensitivity to any component of the formulation of TAK-935.
14. The subject has received any excluded medications, procedures, or treatments during the time periods listed in Section 7.3.

15. The subject has a history of alcohol, opioid, or other drug use disorder, as per the Diagnostic and Statistical Manual of Mental Disorders, Fifth Edition, within the previous 2 years before Screening (Visit 1). Medical marijuana use is allowed.
16. If female, the subject is pregnant or lactating or intending to become pregnant before, during, or within 30 days after participating in this study; or intending to donate ova during such time period.
17. If male, the subject intends to donate sperm during the course of this study or within 30 days after the last dose of study drug.

